## 10.6 Evaluations following each T cell infusion

The following evaluations will be performed after the T cell infusion(s):

- 1) Updated History and physical exam 1 day after the T cell infusion and at least weekly for 3 weeks.
- 2) Laboratory studies:
  - a. CBC, differential, platelet count on day 1,3,7,14, 21 and 28
  - b. Renal, hepatic function with LDH, Mg on day 1,3,7,14, 21 and 28
  - c. Uric acid on day 1,3, and 7
- 3) If a patient becomes febrile or develop symptoms of cytokine release or tumor lysis between the indicated time points, we may measure serum ferritin, IL-6, CRP, DIC panel, and tumor lysis markers at additional times, as clinically indicated.
- 4) Tumor biopsy:
  - a. Patients will also be asked to undergo a biopsy at time of 12 week evaluation and may also be asked to undergo a tumor biopsy at the time of relapse. The goal of the 12 week biopsy will be to confirm that there is progressive/residual tumor if tumors are stable or growing and to confirm that there is residual tumor if tumors are shrinking because a second T cell infusion is not given if there is no residual viable tumor). The purpose of the repeat biopsy at time of late relapse would be to confirm that the relapsed lesion represents metastatic TNBC, urothelial carcinoma or NSCLC. These 12-week and relapse biopsies will be performed for research purposes.
- 5) Research Samples:
  - a. Tumor biopsy: At approximately 14 days following the first T cell infusion, all patients with a palpable or radiologically accessible tumor will be asked to undergo a punch, excisional or a core biopsy. The biopsy at 2 week time point will be for research. The requirement for a biopsy will be waived for patients who do not have tumor amenable to biopsy.
  - b. Research blood samples:
    - i. A 20 ml blood sample (serum separator tube) should be sent to the Specimen Processing/Research Cell Bank Lab at Fred Hutch. Blood samples should be obtained on approximately days 1, 3, 7, 14, 21, and 28 during the first month after each T cell infusion, and also at 2, 3, 6, 9, and 12 months after the T cell infusion
    - ii. A 60 ml blood sample (in EDTA [lavender top] tube) for research should be sent to the Specimen Processing/Research Cell Bank lab. Blood samples should be obtained on approximately days 1, 3, 7, 14, 21, and 28 during the first month after each T cell infusion, and also at 2, 3, 6, 9, and 12 months after the T cell infusion
    - iii. If patients become febrile, develop signs of cytokine release syndrome, or cytokine assessment is clinically appropriate at times other than those indicated, we may collect additional research samples at additional timepoints (optional).

iv. The above research samples will be used in the following ways as described below: for evaluation of serum cytokines, persistence and phenotype of TCR transgenic T cells, evaluation of migration, development, of endogenous anti-tumor immune responses and epitope spreading.

a. Serum storage for measurement of serum cytokine levels

i. Serum cytokine levels will be run at selected time points

b. Evaluation for persistence and phenotype of TCR transgenic T cells

Additional samples may be collected at other times than those indicated, including beyond 12 months, if required for evaluation of persistence of TCR T cells. Conversely, persistence monitoring may be discontinued beyond day 28 after each infusion in patients who do not have detectable transgene-expressing T cells on two consecutive occasions. The cells from these blood samples may also be analyzed by multiparameter flow cytometry for the phenotype of persisting TCR T cells (optional).

c. Evaluation of migration of adoptively transferred TCR T cells

i. Single cell tumor digests will be generated from research biopsy tissue and for selected patients single cell RNA sequencing will be performed (optional).

ii. Multiplex immunohistochemistry will be performed on clinical and/or research biopsies to evaluate T cell localization (optional).

d. Evaluation for development of endogenous anti-tumor immune responses and epitope spreading

We may evaluate whether any cellular or humoral anti-tumor immune responses resulting from activation of endogenous immune cells have occurred. Research samples will be collected; however, performance of research studies is optional and assays may be substituted with alternate assays or omitted as clinical course dictates.

Whole exome sequencing and RNA Seq: For patients in whom endogenous immune responses are detected, more detailed evaluation may be performed to characterize T cell responses by predicting which tumor mutations are likely to be immunogenic and then evaluating peripheral blood T cells for reactivity to these epitopes. To identify mutations and determine the patient's HLA alleles, whole exome sequencing and RNA Seq of baseline tumor as well as whole exome sequencing of normal tissue may be performed (optional).

e. RCL testing

RCL testing, as per FDA guidelines.

v. Leftover materials will be archived for future studies of T cell function. All research assays are optional and may be performed or omitted or replaced with similar studies based on patient's clinical course

## **10.7 Response Assessment**

Participants will have evaluation of tumor burden at baseline (physical exam with tumor measurements, cross-sectional imaging as detailed above, RECIST 1.1 and imRECIST reads of cross-sectional imaging), at approximately 12 weeks after T cell infusion, and then at discretion of treating oncologist (suggested frequency every 3-6 months). *Note:* in patients who receive a second T-cell infusion, repeat baseline imaging should be performed (within 30 days before starting LD chemotherapy or T cell infusion if no LD chemotherapy is given) and again at timepoints outlined above. These assessments have a window of +/- 7 calendar days. Imaging should also be performed if suspicion of progression. Imaging will be performed on a clinical basis with RECIST 1.1/imRECIST reads on a research basis.

Participants will have research biopsy of tumor at baseline, at approximately 12 weeks after first T cell infusion, and if clinically suspected to have progression. Additional research biopsies are planned at 2 weeks post T cell infusion and at 12 weeks after second T cell infusion, and additional research tissue may be requested from clinical biopsies.

## **10.8 Participant discontinuation of active treatment**

A patient will no longer be able to receive active treatment on study (T cells, atezolizumab) for any of the reasons listed below. In this scenario (unless withdrawal of consent or death), a participant will no longer be required to comply with protocol-dictated testing, AE collection, and other timepoints for any of the reasons listed below, with the exception that an attempt will be made to collect samples for RCL and persistence at protocol-dictated timepoints. In this scenario (unless withdrawal of consent or death), the participant will transition to the long term follow up (LTFU) phase of study:

- Progressive disease or development of new metastasis requiring urgent change in treatment following second T cell infusion. Patients can be considered for chemotherapy/radiation for progression between the 1st and second infusions and remain on study if considered appropriate by the PI. Washout between therapies received at time of progression and second lymphodepletion should be either 2 weeks post-radiation or the equivalent of one treatment cycle.
- The participant withdraws consent
- Patient death
- Occurrence of pregnancy
- Participation in another therapeutic trial during the treatment duration of this trial
- Occurrence of an exclusion criterion, which is clinically relevant and affects the subject's safety, if discontinuation is considered necessary by the Investigator or Sponsor
- A patient will no longer be eligible to receive additional therapy if the PI or designee determines that additional T cell infusions are not in the best interest of the patient
- Occurrence of any non-pre-existing grade 3 or higher AEs / repetitive Grade 2 AEDRs that are deemed related to the treatment, except for the exceptions detailed in section 12.

- Cytokine release syndrome requiring pressors for >24 hours or tocilizumab

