### **11.5 Adverse Event Reporting Period**

All adverse events (grades 1-5) will be monitored and recorded in study-specific case report forms (CRFs) throughout the investigative phases of the study: from each T cell infusion through day 14 (for purposes of potential dose modification) and in conjunction with standard follow-up time points during the first year following T cell infusion. The detailed collection of AEs will stop at the time of commencement of new anti-tumor therapy.

AEs with an onset date prior to apheresis will not be recorded, except in the case of clinically significant worsening of the AE during the specified monitoring time frame. A subject withdrawn from the study because of an adverse event must be followed until the clinical outcome from the adverse event is determined.

The following events are *not* identified as AEs in this study:

- Disease progression or relapse.
- Hospitalization to facilitate infusions is not considered an AE. Any AE requiring prolongation of this hospitalization will be recorded and patient to applicable SAE reporting.
- Hospitalization to facilitate monitoring/due to the absence of caregiver/any other reason that is not related to T cells. Medical or surgical procedures in and of themselves, including those that

require hospitalization (e.g., surgery, endoscopy, biopsy procedures) are not considered AEs. However, an event or condition requiring such procedures may be an AE.

- Hospitalization that is otherwise unrelated to adverse events.

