### 12.2 Safety Assessment

#### 12.2.1 Guidelines for Dose Modification

The treatment will be considered to have an acceptable safety profile if the observed DLT rate is consistent with a true rate that does not exceed 35%, and this rate will be used as a guide for decisions related to potential dose modification.

The initial dose level 1 patients will be treated and followed for toxicity for 14 days. Subsequent patients within this group will be able to receive their T cell infusion within 28 days of the last patient receiving their first T cell infusion. Per DAC general guidelines but pending their final recommendation, if zero of the first three dose level 1 patients' experiences treatment-related and unexpected grade  $\geq 3$  toxicity, escalation will proceed to the next dose level. If one patient experiences a treatment-related and unexpected grade  $\geq 3$  toxicity, 3 additional patients will be recruited at the first dose level. If no additional patients experience treatment-related and unexpected grade  $\geq 3$  toxicity, escalation to the next dose level will take place. If 2 or more patients at the first dose level experience treatment-related and unexpected grade  $\geq 3$  toxicity, at the point that the two toxicities occur, the trial will be suspended and, after a detailed review of the potential causes of toxicity, the DAC may consider recommending changing the cell dose pending DSMB review. If any of the dose level 1 patients experience treatment related death, the trial will be suspended and, after a detailed review of the potential causes of toxicity, consideration given to changing the cell dose or construct pending DSMB review. If the DSMB deems safe to re-initiate the protocol, de-escalation will take place (Figure 6) for the second cohort.

If at any point any patient experiences grade 3 or higher unexpected treatment-related toxicity, that particular patient will no longer receive T cell infusions, atezolizumab or other study related active therapies. They will continue to be followed for response and outcome.

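### Section 10.8 ends required AE collection and testing for patients who stop for toxicity, against 12.2.1 and 11.5 and while DLT criteria may still be open

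*Combined protocol and SAP*

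**What the plan says.** Section 10.8 lists the reasons for which a patient receives no more T cells or atezolizumab. Two of them are toxicity:

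- related, non-pre-existing grade 3 or higher events or repetitive grade 2 events, "except for the exceptions detailed in section 12";
- "Cytokine release syndrome requiring pressors for >24 hours or tocilizumab".

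Unless the reason is death or withdrawal of consent, "a participant will no longer be required to comply with protocol-dictated testing, AE collection, and other timepoints for any of the reasons listed below". What remains is that "an attempt will be made to collect samples for RCL and persistence at protocol-dictated timepoints", and "the participant will transition to the long term follow up (LTFU) phase of study".

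Four other places bear on the same patients:

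- **12.2.1** opens its rule with "If at any point any patient experiences grade 3 or higher unexpected treatment-related toxicity". It then stops study therapy for that patient and adds: "They will continue to be followed for response and outcome".
- **11.5** records AEs of all grades from each infusion to day 14 and "in conjunction with standard follow-up time points during the first year following T cell infusion". The only early end it names is the start of new anti-tumor therapy. It also requires a subject withdrawn from the study for an AE to be followed to the outcome of that AE.
- **11.6** lists nine DLT criteria, several of which ask whether an event has resolved some days later.
- **Appendix G** starts long-term follow-up one year after the final infusion. It screens for AEs annually and lists no tumor imaging or RECIST read.

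**The concern.** Patients who stop for toxicity are the ones whose DLT status, AE outcome and response most need to be known. Read literally, 10.8 removes the requirement to collect all three. The event that raises a DLT question can itself end the required AE collection that would answer it.

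Section 11.6 says DLTs guide dose modification, 12.2.1 judges safety against a true DLT rate of 35%, and under 11.7.4 the DAC reviews data after day 28. Efficacy under 12.3 is best overall RECIST response, with three responders as the threshold for success. A patient stopped early for toxicity with no required 12-week read is a gap in that count as well.

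**Working it through.** The plan gives no figure to reproduce here. The check sets the passages side by side, then counts criteria and visits.

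**1. 10.8 against 12.2.1.** Both cover a patient with unexpected related grade 3 or higher toxicity. One lifts required testing and timepoints; the other says response and outcome follow-up continues. The overlap stops there. Expected grade 3 or higher events, repetitive grade 2 events, and CRS treated with tocilizumab that is not an unexpected grade 3 or higher event fall outside the 12.2.1 sentence.

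**2. 10.8 against 11.5.** This applies to every toxicity stop. Section 11.5 runs AE collection through the first year with one early end; 10.8 adds another, triggered by toxicity. The follow-to-outcome duty in 11.5 is worded for a subject withdrawn from the study. A patient moved to another phase of the same study is not clearly that. Section 11.2 lists stop date and outcome among the items to record, but does not say how long a released patient is followed to obtain them.

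**3. DLT criteria that depend on persistence (11.6).** Four of the nine can be read without following the event for a set time: allergic reaction, autoimmune reaction, grade 4 or higher CRS, and PI judgment. The other 9 − 4 = 5 cannot. Each of the five starts from an event at least possibly related to the T cells, which 11.4 counts as related, so it generally meets the 10.8 trigger at onset.

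Assume onset on day d = 1 to 14 and a 10.8 stop the same day. Time for which the criterion is still open:

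| Criterion | Formula | Days open |
|---|---|---|
| Seizure not resolved within 3 days | 3 | 3 |
| Grade 3 CRS not resolved within 7 days | 7 | 7 |
| Neurotoxicity longer than 7 days | more than 7 | just over 7 |
| Non-hematologic, status on day 28 | 28 − d | 27 down to 14 |
| Neurotoxicity, 28 days from infusion | 28 − d | 27 down to 14 |
| Neurotoxicity, 28 days from onset | 28 | 28 |

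The last two rows are one criterion under two readings, since 11.6 does not say where its 28 days start.

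**4. Visits released (Appendix A).** AE assessments after infusion fall on days 1, 3, 7, 14, 21 and 28, six in all. Counting those after the stop day:

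- stop on day 1: 6 − 1 = 5 released
- day 3: 6 − 2 = 4
- day 7: 6 − 3 = 3
- day 14: 6 − 4 = 2

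The persistence row carries the same six days, so AE days and attempted draws coincide on 6 of 6.

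**5. Example (day assumed).** Grade 3 CRS is treated with tocilizumab on day 3. Its criterion is read on day 3 + 7 = 10, between the AE assessments of days 7 and 14, both released. The tocilizumab reason carries no reference to exceptions, so this case does not depend on what the section 12 exceptions are.

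**6. Does long-term follow-up fill the gap?** No. With the Appendix G start date and a single infusion, a patient stopped on day 3 reaches long-term follow-up 365 − 3 = 362 days later. Until then 10.8 keeps only the attempted research draws.

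**The case against.** The strongest reply is that 11.5 already protects the event that matters. All five persistence criteria begin with the event that triggers 10.8, and 11.5 requires an AE leading to withdrawal to be followed to its outcome. If a 10.8 stop counts as withdrawal, most of the DLT gap closes. Section 10.8 can also be read as ending the investigative phase to which 11.5 ties collection. These readings are possible, but the text does not settle them: 10.8 moves the patient to another phase of the study and names AE collection among the things no longer required. At best the 11.5 duty covers the triggering AE, not other AEs or response.

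Other points stand as limits:

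- Section 10.8 lifts a requirement and does not forbid collection. Staff may still abstract AEs under 11.7.4.
- SAE reporting in 11.7 is not expressly waived. It is event reporting, however, and does not replace scheduled AE or response assessment.
- Imaging is clinical under 10.7, so an existing scan can still be read.
- DAC and DSMB review remain, and the numeric escalation rule in 12.2.1 counts unexpected related grade 3 or higher events with no persistence test.
- In the example, no AE visit falls on day 10 even without 10.8. The later visits help by capturing the stop date.
- A same-day stop is a worst case, since the event must first be judged related. The section 12 exceptions could narrow the trigger; section 12 contains no list of them, though its restriction to unexpected toxicity may be what is meant.

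**Conclusion.** The concern holds. Section 10.8 contradicts 12.2.1 for unexpected related grade 3 or higher toxicity and conflicts with 11.5 for all toxicity stops. It can release a patient from AE collection while any of five of the nine DLT criteria is undecided. Under the same-day assumption, criteria stay open for 3 to 28 days, and 2 to 5 of the six AE assessments through day 28 are released for stops on days 1 to 14.

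The documents do not say how often 10.8 would apply, and no change in a dose decision or in power is demonstrated. The protocol sections ahead of the baseline evaluations in section 10 were not available and may contain further follow-up provisions. The point merits an amendment because the rule, followed as written, gives poorer safety and response data in these patients.

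**What to change.** Amend 10.8 so that patients who stop treatment for toxicity:

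- keep AE collection at the visits already scheduled until every open DLT criterion can be read and the AE outcome is known, in line with 11.5;
- keep the 12-week RECIST read of the clinical scan, in line with 12.2.1 and 10.7.

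Reconcile the immediate move to long-term follow-up in 10.8 with the one-year start in Appendix G, and state which section 12 exceptions 10.8 refers to. None of this sets a dose or a treatment rule.

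The cost is protocol wording and a little extra data collection. Through day 28 no visit is added where the attempted persistence draw takes place. After day 28, 10.6 lets persistence monitoring end after two consecutive negative results, so an AE still open then would need its own contact.

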### **10.9 Long-term follow-up**

Enrolled patients who receive FH-MagIC TCR-T will be asked to participate in long-term follow-up (LTFU) according to guidelines set forth by the FDA's Biologic Response Modifiers Advisory Committee that apply to gene transfer studies. Current recommendations from the FDA suggest a minimum of 15 years of follow-up.

Should the participant develop a late relapse, a 50 ml blood draw and/or leftover/excess biopsy tissue (fresh and/or archival) will be requested for evaluation as to mechanisms of late relapse.

Recommendations will be made for an autopsy to be conducted if the research participant dies.

## **11.0 ADVERSE EVENT REPORTING**

### **11.1 Adverse Event Definitions**

- **Adverse Event**

An Adverse Event (AE) is any untoward medical occurrence in a clinical investigation subject administered a medicinal product; the event does not necessarily have a causal relationship with study drug administration or usage. An adverse event can therefore be any unfavorable and unintended sign (including an abnormal laboratory finding), symptom, or disease temporally associated with the use of a medicinal product, whether or not considered related to the medicinal product.

- **Serious Adverse Event**

A serious adverse event (SAE) is defined as an untoward medical occurrence that results in any of the following outcomes:

1. Death.
2. Life-threatening situation (i.e., with an immediate risk of death from the event as it occurred but not including an event that, had it occurred in a more serious form, might have caused death).
3. In-patient hospitalization or prolongation of existing hospitalization. Inpatient hospitalization comprises formal admission to a hospital for medical reasons, for any length of time, whether or not hospitalization extends overnight. However, hospital admissions for administration of the study drug, procedures required by the study protocol, or tumor-related diagnostic procedures are not considered serious.
4. Persistent or significant disability/incapacity or substantial disruption of the ability to conduct normal life functions.
5. Congenital anomaly/birth defect.
6. An important medical event that requires intervention to prevent one of the above outcomes.

- **Unexpected Adverse Event**

An unexpected adverse event is defined as an event that has a nature or severity, or frequency that is not consistent with the investigator brochure, protocol, or consent form. Please see section 11.6 for expected toxicities.

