### **11.2 Monitoring and Recording Adverse Events**

Adverse events will be assessed by the investigator or qualified designee and recorded in the CRFs. The investigator should attempt to establish a diagnosis of the event on the basis of signs, symptoms and/or other clinical information. In such cases, the diagnosis should be documented as the adverse event and/or serious adverse event and not described as the individual signs or symptoms. The following information should be recorded:

- Description of the adverse event using concise medical terminology
- Description as to whether or not the adverse event is serious
- The start date (date of adverse event onset)
- The stop date (date of adverse event resolution or return to baseline)
- The severity (grade) of the adverse event
- A description of the potential relatedness of the adverse event to study drug or a study procedure
- Expectedness of the adverse event based on prior observed and documented adverse events
- The outcome of the adverse event

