## **11.6 Dose-limiting Toxicities to Guide Dose Modification**

Dose-limiting toxicity (DLT) is defined as below and will be used to guide potential dose modification as detailed in **Sections 11.7.4 and 12.2.1**.

DLTs will be assessed for 14 days following the first infusion of the TCR-T cell product. The following events will be considered DLTs if they are attributed as at least possibly related to T cell administration. Grading will be done in accordance with the NCI Common Terminology Criteria for Adverse Events ([CTCAE Version 5.0](#) unless otherwise specified.

- Grade  $\geq$  3 allergic reaction related to the TCR-T cell infusion
- Grade  $\geq$  3 autoimmune reactions
- Any Grade 3 or 4 non-hematologic event that has not resolved to < grade 3 by day 28 post T cell infusion
- Grade  $\geq$  3 neurotoxicity of greater than 7 days duration
- Grade  $\geq$  3 neurotoxicity that does not revert to Grade 1 or baseline within 28 days
- Grade  $\geq$  3 seizures that do not resolve to < grade 3 within 3 days
- Grade  $\geq$  4 CRS (using criteria modified from Lee 2014)
- Grade 3 CRS that does not resolve to < grade 3 within 7 days
- Any other toxicity not meeting the above criteria that is deemed by the PI to represent a DLT

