#### **11.7.3 Institution-Sponsor Reporting Requirements**

The sponsor assumes responsibility for IND safety reporting to the FDA and participating investigators, in accordance with regulations under 21 CFR 312.32.

Each serious adverse event report received from the investigator will be evaluated by the Medical Monitor who will assess the seriousness of the event, the expectedness of the event, and the relationship to participation in the study. For regulatory reporting purposes, the IND Sponsor will determine expectedness relating to the investigational product using safety information specified in the Investigator Brochure. An event will be classified as related if either the investigator or the IND Sponsor determines that the event may be related to the study drug.

The IND Sponsor or designee will provide all investigators with a safety letter notifying them of an event that meets FDA IND Safety Reporting criteria. Investigators will be requested to provide written notification of safety report to the Fred Hutch IRB as soon as is practical, consistent with IRB requirements.

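### Section 11.1 points to the DLT list for expected toxicities, while the dose level 1 steps count only unexpected toxicities

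*Combined protocol and SAP*

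**What the plan says.** The definition is in section 11.1: "An unexpected adverse event is defined as an event that has a nature or severity, or frequency that is not consistent with the investigator brochure", with the protocol and the consent form as further references. It then adds: "Please see section 11.6 for expected toxicities".

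Section 11.6 is titled "Dose-limiting Toxicities to Guide Dose Modification". It contains the DLT list and no list of expected toxicities. Its opening sentence reads "Dose-limiting toxicity (DLT) is defined as below and will be used to guide potential dose modification as detailed in" sections 11.7.4 and 12.2.1.

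Section 12.2.1 opens with a benchmark DLT rate of 35%, but its dose level 1 steps count a different event, namely toxicity of grade 3 or higher that is both related and unexpected:

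- None in the first three patients: escalate.
- One in three: add three patients, and escalate if there are no more.
- The suspension step begins "If 2 or more patients at the first dose level experience treatment-related and unexpected grade" 3 or higher toxicity.

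The same filter decides, in 12.2.1, whether an individual patient stops study therapy.

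Expectedness appears in two other places. Section 11.2 lists among the items to record "Expectedness of the adverse event based on prior observed and documented adverse events". Section 11.7.3 says, for regulatory reporting, that "the IND Sponsor will determine expectedness relating to the investigational product using safety information specified in the Investigator Brochure".

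**The concern.** If 11.6 is where expected toxicities are found, then the events on it (grade 4 or higher CRS, prolonged grade 3 or higher neurotoxicity, and so on) are expected. The steps in 12.2.1 would then ignore the very events that 11.6 says should guide them. Related grade 3 events too short-lived to be on the list could still count, so the more serious events would be the ones left out.

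The 11.2 field raises a second, softer problem. It does not say where or when the earlier events were observed. If events earlier in this trial qualify, a toxicity seen in one patient could be recorded as expected when it recurs in the next. Two patients with the same severe toxicity would then supply only one countable event.

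At stake is the rule at the first dose level: whether three patients are added, whether the trial moves up, and whether it is suspended.

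**Working it through.** **Inputs.** The steps, the 35% benchmark and the excess-toxicity boundary (2/2, 3/3-4, 4/5-6, up to 9/15) all come from 12.2.1. The share u of related grade 3 or higher events that would be called unexpected is not given. It is an assumption, varied here from 100% to 0%.

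**The plan's own figure.** Section 12.2.1 gives suspension probabilities of about 0.06 at a 20% true rate and 0.84 at 60% for the boundary. An exact binomial recursion, with the boundary checked after every patient from 2 to 15, gives 0.062 and 0.824, within two percentage points of both. Those figures describe the boundary only, not the dose level 1 steps.

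**Dose level 1 steps, every event counted.** With p the probability of a counted event per patient and q = 1 − p:

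P(escalate) = q³ + 3pq² × q³, and P(suspend) = 1 − P(escalate).

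- p = 0.35: 0.2746 + 0.4436 × 0.2746 = 0.396; suspend 0.604.
- p = 0.40: 0.2160 + 0.4320 × 0.2160 = 0.309; suspend 0.691.
- p = 0.60: 0.0640 + 0.2880 × 0.0640 = 0.082; suspend 0.918.

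**True rate 35%, only a share u counted.** Replace p by 0.35 × u:

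| u | counted rate | escalate | suspend |
|---|---|---|---|
| 100% | 0.350 | 0.396 | 0.604 |
| 75% | 0.2625 | 0.573 | 0.427 |
| 50% | 0.175 | 0.762 | 0.238 |
| 25% | 0.0875 | 0.926 | 0.074 |
| 0% | 0 | 1.000 | 0 |

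**Repeats treated as expected (one reading of 11.2).** Assume T equally likely toxicity types, and that a type already seen no longer counts:

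P(escalate) = q³ + [3pq² + 3p²q/T + p³/T²] × [1 − p(T − 1)/T]³.

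At p = 0.35:

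- T = 2: 0.2746 + 0.5738 × 0.5615 = 0.597.
- T = 3: 0.2746 + 0.5280 × 0.4506 = 0.513.
- T = 5: 0.2746 + 0.4931 × 0.3732 = 0.459.

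All compare with 0.396 when repeats count. With a single type the count cannot reach two, which is the extreme case.

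**The unfiltered boundary at 35%, every event counted.**

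- Events in both of the first two patients: 0.35² = 0.1225. This is also the figure within three patients, because 3/3 requires 2/2.
- One event in the first two, then two more (3/4): 2 × 0.35 × 0.65 × 0.1225 = 0.0557.
- Two events in four, not both in the first two, then two more (4/6): 5 × 0.35² × 0.65² × 0.1225 = 0.0317.
- Total within six patients: 0.1225 + 0.0557 + 0.0317 = 0.21.

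So the boundary restores part of the protection, but 0.12 to 0.21 is well short of 0.60. If nothing counts under the steps, dose level 1 closes after three patients, and the 0.12 figure is the relevant one there.

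**The case against.** The strongest reply is that the pointer is simply a stale cross-reference. The main clause of 11.1 defines unexpectedness by the brochure, protocol and consent form. Section 11.6 says that DLTs guide dose modification, and 12.2.1 opens with a DLT rate, so the authors can hardly have meant to exclude DLTs. This is probably right about intent. It does not cure the text, because the protocol is itself one of the references for expectedness, and the sentence in it points to the DLT list.

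A reader might go further and infer three competing standards of expectedness. The documents do not support that: 11.7.3 is limited to regulatory reporting, and 11.2 lists items to record and does not define the term.

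A reader might also infer that any repeat of an earlier toxicity is automatically expected. Section 11.2 does not say that the earlier events must come from this trial, and it could equally mean previous product experience. Section 11.1 also keeps severity and frequency as grounds for calling an event unexpected.

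Finally, several safeguards carry no expectedness filter: the excess-toxicity boundary, suspension for treatment-related death at dose level 1, DSMB review of all grade 3 or higher toxicities (13.2), and the discretion of the Dose Assessment Committee (11.7.4, 12.2.1, Appendix H). Section 10.8 has a patient-level stop for related grade 3 or higher events without this filter, though subject to exceptions in section 12. All of this stands and limits the harm. None of it settles what the dose level 1 steps count.

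**Conclusion.** The cross-reference is wrong as written, and it feeds a safety count. Taken literally, 11.1, 11.6 and 12.2.1 together remove the listed DLTs from the dose level 1 decisions they are supposed to guide. The 11.2 field is ambiguous and could remove repeats as well.

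The size depends on the unstated share of events that would be called unexpected. At a 35% true rate, suspension under the steps ranges from 0.60 when all count down to 0 when none do. The zero is a bounding case: it needs every related grade 3 or higher toxicity to be labelled expected, and it concerns the two-event step alone. It would be wrong to conclude that the trial could not be suspended.

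This should be fixed. Confidence is moderate, because the text available here begins within section 10 and does not include the brochure, so a list of expected toxicities may exist elsewhere. Even then, the pointer to 11.6 would still need correcting.

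**What to change.** Three changes, all of wording:

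1. Correct the cross-reference in 11.1 so that it no longer labels the DLT list as expected toxicities.
2. Reconcile 11.1, 11.2, 11.6 and 12.2.1 so that the dose level 1 steps rest on one stated counted event and one named expectedness reference for dose decisions. The patient-level stops in 10.8 and 12.2.1 should be read against each other at the same time.
3. State whether an occurrence within this trial can make a later event expected.

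Which events should count, and which reference applies, are for the sponsor to decide. The cost is a short amendment and possibly more events counting toward suspension. Once the counted event is settled, the operating characteristics of the steps can be stated beside those already given for the boundary.
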